#### 11.2.2. Primary End Point Analysis

The primary end point is the proportion (frequency and percentage) of men with a screen-positive MRI defined by a score of 3 or greater. The proportion of men with a positive radiological score will be reported along with the corresponding 95% confidence intervals. This analysis will be repeated for PIRADS cut-off [1] and Likert cut-off [1], as defined in Section 10.3.1.

#### 11.2.3. Other Test Performance (MRI and US) End Point Analysis

The proportion of men with a screen-positive MRI defined by a score of 4 or greater will be reported. This analysis will be repeated for PIRADS cut-off [2] and Likert cut-off [2], as defined in Section 10.3.1.

The proportion of men with a screen-positive prostate ultrasound score (US), using the two US cut-offs for a screen-positive result defined in Section 10.3.2, will be reported. Similarly, the proportion of patients with a raised PSA level, using the definition in Section 10.3.3, will be reported.

The proportions of patients within each discrete score of the Likert, PIRADS and US scoring systems (see Sections 10.3.1 & 10.3.2) will be reported. The distribution of patients across the discrete scores will be displayed using a histogram for each scoring system.

The proportions of patients across the discrete values of the scoring systems for MRI and ultrasound detected to have clinically significant cancer, clinically insignificant cancer or no cancer, by each screening test (repeated for each of the thresholds defined in Section 8.1 separately) will be reported. The distribution of the type of cancer detected by each test, using each definition ((i)-(v), Section 8.1), will be displayed using histograms for each scoring system. Similarly, the proportions of patients with raised and normal PSA (see Section 10.3.3) detected to have clinically significant cancer, clinically insignificant cancer or no cancer (repeated for each of the thresholds defined in Section 8.1 separately) will be reported.

Comparisons of proportions of screening results (positive/negative), between pairs of screening tests, (MRI & ultrasound, MRI & PSA, ultrasound & PSA) will be conducted using McNemar chi square tests. McNemar chi square tests will be used to assess whether there is marginal homogeneity of results between pairs of screening tests. The McNemar chi square test statistic and p-value will be reported for each pair of screening results. This analysis will use the screen-positive MRI cut-offs defined by the PIRADS scoring system (see Section 10.3.1), and the screen-positive ultrasound cut-offs defined by the US scoring system (see Section 10.3.2).

Sensitivity and specificity analysis will be conducted between screening test results and histology results (reference standard). Histology results will be dichotomised into "clinically significant cancer" and "absence of clinically significant cancer" (repeated for each of the threshold definitions in Section 8.1). The following measures of test accuracy will be reported, along with

Imperial Clinical Trials Unit	STATISTICAL ANALYSIS PLAN	PROSTAGRAM
----------------------------------	---------------------------	------------

their 95% confidence intervals: negative predictive value (NPV), positive predictive value (PPV), sensitivity and specificity. Results will be displayed using graphs for each screening test.

The proportions of false positive results will be reported, with histology as reference. This analysis will be repeated for each of the definitions of false positive results outlined in Section 10.3.8.

For each HDP (see Section 8.3) the proportion of participants with all positive tests, along that pathway, will be reported. For each HDP, we will take the population of participants with all positive tests along each pathway and provide summary statistics. Screen-positive results for MRI are defined by PIRADS cut-off [2] in Section 10.3.1. Similarly, screen-positive results for ultrasound are defined by US cut-off [2] in Section 10.3.2. A “positive” PSA result is defined by a raised PSA level ( $\geq 3.0\text{ng/ml}$ ) (see Section 10.3.3). The summary statistics will be in terms of: the total number of patients who were biopsied (see Section 10.3.5), the total number of patients who were detected to have clinically insignificant cancer in targeted and non-targeted cores, separately, and, the total number of patients who were detected to have clinically significant cancer in targeted and non-targeted cores, separately. This analysis will be limited to the generally accepted definitions for the detection of clinically significant and insignificant cancers (definitions (i) in Sections 8.1.1 & 8.1.2) (7), only.

The proportions of patients, with positive test results by each screening test, who go onto local or systemic treatment for prostate cancer (see Section 10.3.6) will be reported. Positive screening test results will be defined using the PSA cut-off in Section 10.3.3, and both PIRADS and US cut-offs in Sections 10.3.1 & 10.3.2.

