2.14 Specification of efficacy parameters

OBJECTIVES		EFFICACY PARAMETER	TIME POINT & TOOL
Primary Objectives			
To determine the prevalence of screen-positive prostate MRI scans in the general male population aged 50 to 69 years		The proportion of men with a screening MRI score of 3 or greater	Visit 1 MRI reporting form
Secondary Objectives			
OTHER TEST PERFORMANCE OBJECTIVES (MRI AND US)	To determine the prevalence of positive test rate of US	The proportion of men with a screening US score of 3 or greater	Visit 1: US reporting form
	To establish the distribution of MRI and US scores in a screened population	The proportion of men across each MRI score	Visit 1: MRI & US reporting form
	To establish a threshold score that defines positivity of MRI and US in a screened population	Comparison of false positives & false negatives across each MRI & US scores	Visit 1 & 2: MRI, US and biopsy reporting form
	The overall agreement between PSA, US and MRI in the proportion of men with a screen positive result.	The proportion with a positive result for each screening test	Visit 1 PSA, US and MRI reporting form
	The overall agreement between PSA, US & MRI in proportion of men diagnosed with clinically significant prostate cancer on biopsy.	The proportion diagnosed with a clinically significant prostate cancer as defined histologically	Visit 1 & 2: PSA, MRI and biopsy reporting form
	To explore combinations & sequences of MRI, US and PSA	Comparison of biopsy rates, detection of insignificant/significant cancer	Visit 1 PSA, MRI, US reporting form
	To estimate overall imaging findings and DRE	Correlation between imaging & DRE	Visit 1 & 2 MRI, US & DRE form
	To report the clinical outcomes of men with any positive test result	The proportion who undergo treatment. If RRP the proportion upgraded at final histology	Visit 1-3: PSA, MRI and biopsy reporting form. Treatment outcomes

IP1 - PROSTAGRAM	Protocol No: 18HH4595	Sponsor: Imperial College London	V 1.2 01MAY2019
-------------------------	---------------------------------	--	------------------------

OBJECTIVES		ENDPOINT	TIME POINT & TOOL
FLUIDIC BIOMARKERS	To establish the positive test rate and distribution of biomarker panel scores	The proportion of men with a positive Episwitch biomarker panel and score	Visit 1: Biomarker panel reporting form

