### 3.2. Secondary Objectives

#### 3.2.1. Other Test Performance Objectives (MRI and US)

1. To determine the prevalence of positive test rate of prostate ultrasound in the general male population aged 50 to 69 years
2. To determine the distribution of MRI and US scores in a screened population
3. To evaluate a suitable threshold score that defines positivity of MRI or US in a screening population
4. To estimate the overall agreement between PSA, US and MRI in the proportion of men with a positive result. Then to compare the overall agreement in proportion of men diagnosed with clinically significant prostate cancer on biopsy.
5. To explore combinations and sequences of prostate MRI, US and PSA that might be an optimal screening strategy to evaluate in a future definitive study
6. To estimate the overall agreement of Imaging findings, PSA and DRE
7. To report the clinical outcomes of men with a positive PSA, US and/or MRI result.

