### 4.2. Secondary End Points

#### 4.2.1. Other Test Performance End Points (MRI and US)

1. The proportions of men with a screen-positive MRI defined by a score of 4 or greater (Likert and PIRADS)
2. The proportion of men with screen-positive prostate ultrasound defined by a score of 3 or greater (US)
3. The proportion of men with screen-positive prostate ultrasound defined by a score of 4 or greater (US)
4. The proportion of men with raised PSA result defined by a recorded level of 3 ng/mL or greater
5. The proportion of participants within each MRI score or US score of 1, 2, 3, 4 or 5
6. An evaluation of proportion of participants across each MRI and US score with no cancer, insignificant cancer and significant cancer with each test
7. The proportion of participants across each PSA level (raised or normal) with no cancer, insignificant cancer and significant cancer
8. A comparison of the proportion of participants with a positive result for each screening test. A comparison of the proportion of men subsequently diagnosed with a clinically significant prostate cancer as defined by pre-specified histological definitions
9. Comparison of different testing combinations in terms of biopsy rates, detection of insignificant cancer and significant cancers
10. The correlation between imaging findings and DRE
11. The proportion of men who go onto definitive local or systemic treatment.

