----------------------------------	---------------------------	------------

	
 
Proportion within each value of US score detected to have each type of clinical cancer (Sections 8.1 & 10.3.2)
 
Histograms of distribution of type of cancer detected across scoring systems
 
	respective analyses 
Proportion of participants with raised and normal PSA level with no cancer, insignificant cancer and significant cancer	Proportion with raised and normal PSA result detected to have each type of clinical cancer (Sections 8.1 & 10.3.3)	Participants biopsied, and who have PSA results 
Comparison of the proportion of participants with a positive result for each screening test	
Comparisons of proportions of results (positive/negative) between pairs of screening tests:
 
 
MRI & ultrasound
 
MRI & PSA
 
Ultrasound & PSA
 
 
using McNemar chi square tests
	Participants who completed both tests in each pair 
Comparison of the proportion of men subsequently diagnosed with a clinically significant prostate cancer (as defined by pre-specified histological definitions)	
 
Sensitivity and specificity of screening results (MRI, ultrasound and PSA) with histology results as reference standard (Sections 10.3.1, 10.3.2 and 10.3.3)
 
Graph displaying proportions of results for each screening test compared to histology results
 
Proportions of false positive results by each screening test (MRI, ultrasound and PSA), using histology (no cancer) as the reference
 
Proportions of false positive results by each screening test (MRI, ultrasound and PSA), using histology (no cancer or Gleason 3+3) as the reference
 
	Participants biopsied, and who completed the relevant test for the respective analysis 

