**Table 1.2. 7: Proportion of men within each value of the discrete PIRADS score (MRI scoring system) and corresponding type of clinical cancer detected**

See Table 1.2. 6, but for discrete values of the PIRADS scoring system.

See Section 8.1 for definitions.

**Table 1.2. 8: Proportion of men within each value of the discrete ultrasound score (US) and corresponding type of clinical cancer detected**

See Table 1.2. 6, but for discrete values of the US scoring system.

See Section 8.1 for definitions.

**Table 1.2. 9: Proportion of men within each PSA level (raised and normal) and corresponding type of clinical cancer detected**

Definition 	Type of clinical cancer	PSA Level	
		Raised ( $\geq 3.0$ ng/ml)	Normal ( $< 3.0$ ng/ml)
i	Clinically significant cancer	xxx (xx%) x.xx to x.xx	xxx (xx%) x.xx to x.xx
	Clinically insignificant cancer	xxx (xx%) x.xx to x.xx	xxx (xx%) x.xx to x.xx
	No cancer	xxx (xx%) x.xx to x.xx	xxx (xx%) x.xx to x.xx
ii	Clinically significant cancer	xxx (xx%) x.xx to x.xx	xxx (xx%) x.xx to x.xx
	Clinically insignificant cancer	xxx (xx%) x.xx to x.xx	xxx (xx%) x.xx to x.xx
	No cancer	xxx (xx%) x.xx to x.xx	xxx (xx%) x.xx to x.xx
iii	Clinically significant cancer	xxx (xx%) x.xx to x.xx	xxx (xx%) x.xx to x.xx
	Clinically insignificant cancer	xxx (xx%) x.xx to x.xx	xxx (xx%) x.xx to x.xx
	No cancer	xxx (xx%) x.xx to x.xx	xxx (xx%) x.xx to x.xx
iv	Clinically significant cancer	xxx (xx%) x.xx to x.xx	xxx (xx%) x.xx to x.xx

	Clinically insignificant cancer	xxx (xx%) x.xx to x.xx	xxx (xx%) x.xx to x.xx
	No cancer	xxx (xx%) x.xx to x.xx	xxx (xx%) x.xx to x.xx
v	Clinically significant cancer	xxx (xx%) x.xx to x.xx	xxx (xx%) x.xx to x.xx
	Clinically insignificant cancer	xxx (xx%) x.xx to x.xx	xxx (xx%) x.xx to x.xx
	No cancer	xxx (xx%) x.xx to x.xx	xxx (xx%) x.xx to x.xx

See Section 8.1 for definitions.

See Section 10.3.3 for definitions.

**Table 1.2. 10: Comparisons of proportions of results between pairs of screening tests (MRI & ultrasound, MRI & PSA and ultrasound & PSA) using McNemar chi square tests**

McNemar's test statistic		MRI		Ultrasound		PSA
		Positive MRI (PIRADS ≥ 3) (Cut-off [1])	Positive MRI (PIRADS ≥ 4) (Cut-off [2])	Positive ultrasound (US ≥ 3) (Cut-off [1])	Positive ultrasound (US ≥ 4) (Cut-off [2])	Raised PSA (≥ 3.0 ng/ml)

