MRI	Positive MRI (PIRADS ≥ 3) (Cut-off [1])			McNemar's chi2(1) = xx.xx p-value = x.xxx	McNemar's chi2(1) = xx.xx p-value = x.xxx	McNemar's chi2(1) = xx.xx p-value = x.xxx
	Positive MRI (PIRADS ≥ 4) (Cut-off [2])			McNemar's chi2(1) = xx.xx p-value = x.xxx	McNemar's chi2(1) = xx.xx p-value = x.xxx	McNemar's chi2(1) = xx.xx p-value = x.xxx
Ultrasound	Positive ultrasound (US ≥ 3) (Cut-off [1])	McNemar's chi2(1) = xx.xx p-value = x.xxx	McNemar's chi2(1) = xx.xx p-value = x.xxx			McNemar's chi2(1) = xx.xx p-value = x.xxx
	Positive ultrasound (US ≥ 4) (Cut-off [2])	McNemar's chi2(1) = xx.xx p-value = x.xxx	McNemar's chi2(1) = xx.xx p-value = x.xxx			McNemar's chi2(1) = xx.xx p-value = x.xxx
PSA	Raised PSA (≥ 3.0 ng/ml)	McNemar's chi2(1) = xx.xx p-value = x.xxx	McNemar's chi2(1) = xx.xx p-value = x.xxx	McNemar's chi2(1) = xx.xx p-value = x.xxx	McNemar's chi2(1) = xx.xx p-value = x.xxx	

See Section 10.3.1, 10.3.2 and 10.3.3 for definitions

Screen-positive vs screen-negative results by each threshold definition

**Table 1.2. 11: Sensitivity and specificity of screening results (screen-positive or screen-negative) with histology results (clinically significant cancer vs absence of clinically significant cancer) as reference standard**

	Screening results
--	--------------------------------------

		Positive MRI (PIRADS $\geq 3$ ) (Cut-off [1])	Positive MRI (PIRADS $\geq 4$ ) (Cut-off [2])	Positive ultrasound (US $\geq 3$ ) (Cut-off [1])	Positive ultrasound (US $\geq 4$ ) (Cut-off [2])	Raised PSA ( $\geq 3.0$ ng/ml)
Prevalence		xxx (xx%)	xxx (xx%)	xxx (xx%)	xxx (xx%)	xxx (xx%)
Definitions of clinically significant cancer	i	Sens = Spec = PPV = NPV =	Sens = Spec = PPV = NPV =	Sens = Spec = PPV = NPV =	Sens = Spec = PPV = NPV =	Sens = Spec = PPV = NPV =
	ii	Sens = Spec = PPV = NPV =	Sens = Spec = PPV = NPV =	Sens = Spec = PPV = NPV =	Sens = Spec = PPV = NPV =	Sens = Spec = PPV = NPV =
	iii	Sens = Spec = PPV = NPV =	Sens = Spec = PPV = NPV =	Sens = Spec = PPV = NPV =	Sens = Spec = PPV = NPV =	Sens = Spec = PPV = NPV =
	iv	Sens = Spec = PPV = NPV =	Sens = Spec = PPV = NPV =	Sens = Spec = PPV = NPV =	Sens = Spec = PPV = NPV =	Sens = Spec = PPV = NPV =
	v	Sens = Spec = PPV = NPV =	Sens = Spec = PPV = NPV =	Sens = Spec = PPV = NPV =	Sens = Spec = PPV = NPV =	Sens = Spec = PPV = NPV =

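### The objective is to estimate agreement between PSA, ultrasound and MRI, but the pairwise analysis reports only a McNemar chi-square and p-value, which neither measure agreement nor give a paired effect estimate

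*SAP*

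**What the plan says.** The objective, in the same words in protocol 2.2 and SAP 3.2.1, begins "To estimate the overall agreement between PSA, US and MRI in the proportion of men with a positive result". The end point that answers it in SAP 4.2.1 is "A comparison of the proportion of participants with a positive result for each screening test", and the efficacy parameter against it in protocol 2.14 is "The proportion with a positive result for each screening test".

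SAP Table 1 analyses this end point for MRI and ultrasound, MRI and PSA, and ultrasound and PSA, in the population "Participants who completed both tests in each pair". Section 11.2.3 states the purpose: "McNemar chi square tests will be used to assess whether there is marginal homogeneity of results between pairs of screening tests". It then states the output: "The McNemar chi square test statistic and p-value will be reported for each pair of screening results". Table 1.2.10, titled "Comparisons of proportions of results between pairs of screening tests", carries in every filled cell "McNemar's chi2(1) = xx.xx p-value = x.xxx" and nothing more.

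Two other tables bear on the question. Table 1.2.2 gives each test's positive rate, at each cut-off, with a 95% confidence interval. Table 1.2.14 gives, for hypothetical pathways that include PSA with MRI, PSA with ultrasound, and ultrasound with MRI, the proportion positive on every test in the pathway, using cut-off [2] for MRI and ultrasound. Cohen's kappa with a confidence interval is planned in SAP 11.5, but only between the local and central MRI readers.

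**The concern.** Agreement between two tests depends on how many men are positive on both and negative on both. McNemar uses only the two discordant cells and asks whether they are equal. The objective asks for an estimate, and the planned pairwise output contains none: no cross-tabulation, no difference, no interval, no agreement measure.

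The stated long-term question (protocol 1.4, SAP 2.6) is whether MRI might replace PSA or add to it. Overlap between the tests is part of the evidence on that. The study is also meant to inform the design of a larger paired study of PSA and MRI (protocol 1.4), and sizing a paired comparison needs estimates of the discordant cells. A chi-square and a p-value do not supply them directly.

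**Working it through.** **Planning figures (protocol 9.1).** PSA raised: 10.4%. Positive on both PSA and MRI: 73% × 10.4% = 7.59%. MRI-positive overall: 11.98% + 7.59% = 19.6% (low scenario), or 53.54% + 7.59% = 61.1% (high scenario).

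**The plan's sample sizes.** n = 1.96² × P(1−P) / 0.05². P = 0.196 gives 242.1, so 243; P = 0.611 gives 365.2, so 366. Both match. I take 366 as the number with both MRI and PSA; this is an assumption.

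**2x2 tables, MRI against PSA, as percentages of men.** With both-positive a = 7.59, MRI-only b = MRI rate − a, PSA-only c = 10.4 − 7.59 = 2.81, and neither d = the remainder:
- Low: a 7.59, b 12.01, c 2.81, d 77.59.
- High: a 7.59, b 53.51, c 2.81, d 36.09.

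**Formulas**, with a to d as proportions:
- McNemar chi-square = n(b−c)²/(b+c). No continuity correction is used, as the SAP states none.
- Paired difference D = b−c, with SE = √[(b+c−D²)/n].
- Overall agreement = a+d. Positive agreement = 2a/(2a+b+c).
- Kappa = (a+d−pe)/(1−pe), where pe is the agreement expected by chance from the margins.

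**Low scenario.**
- Chi-square = 366 × 0.092² / 0.1482 = 20.9, p = 5×10⁻⁶.
- D = 9.2 points, SE 1.95 points, 95% CI 5.4 to 13.0.
- Overall agreement = 7.59 + 77.59 = 85.2%. Positive agreement = 15.18/30.0 = 51%.
- pe = 0.741, kappa = (0.852 − 0.741)/0.259 = 0.43.

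**High scenario.**
- Chi-square = 366 × 0.507² / 0.5632 = 167, p = 3×10⁻³⁸.
- D = 50.7 points, SE 2.89 points, 95% CI 45.0 to 56.4.
- Overall agreement = 7.59 + 36.09 = 43.7%. Positive agreement = 15.18/71.5 = 21%.
- pe = 0.412, kappa = (0.437 − 0.412)/0.588 = 0.04.

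Table 1.2.10 prints p-values to three decimals, so both scenarios would show the same p-value.

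**Overlap varied, margins fixed.** This keeps the low-scenario margins (19.6% and 10.4%, n = 366). Only the second row is the protocol's planning case; the others are illustrative.

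| Both positive | Chi-square | p | D (points) | Kappa |
|---|---|---|---|---|
| 10.4% (all PSA-positives) | 33.7 | 7×10⁻⁹ | 9.2 | 0.65 |
| 7.59% | 20.9 | 5×10⁻⁶ | 9.2 | 0.43 |
| 2.04% (chance: 0.196 × 0.104) | 11.9 | 5×10⁻⁴ | 9.2 | 0.00 |

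The difference in rates never changes, yet the p-value becomes smaller as agreement improves. A small p-value therefore cannot be read as poor agreement.

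The documents give no planning rate for ultrasound, so I have not computed its pairs.

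**The case against.** The best defence is that the objective speaks of agreement in the proportion positive, and that protocol 2.14 and SAP 4.2.1 turn this into a comparison of positive proportions. McNemar is the standard paired test for that, and the SAP names exactly what it tests. This stands as a defence of the test: a reader might infer that McNemar is the wrong choice, and the documents do not support that. It does not supply the estimate that the objective asks for.

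A reader might also infer that the plan gives no effect size anywhere. It does give some. Table 1.2.2 shows every positive rate with an interval, so a crude difference can be taken by hand, and Table 1.2.14 shows joint positives for some pairs. But Table 1.2.2 counts men with that single test, not men with both. Table 1.2.14 uses cut-off [2], not the primary end point's cut-off [1], and SAP Table 1 gives its population as biopsied men. Where every man had both tests, the discordant total could even be recovered as (b−c)²/chi-square; in the low scenario, 33.7²/20.9 = 54 men. That fails when denominators differ or the two rates are equal, and readers should not have to do it.

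A third tempting inference is that a non-significant p-value will be taken to mean that the tests agree. On the planning figures this would not arise for MRI against PSA, where both scenarios are highly significant.

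Finally, agreement measures contain no cancer outcome, so they cannot by themselves settle whether imaging should replace PSA or be added to it. The pathway analysis addresses test combinations. Kappa also depends on prevalence. Both points stand, and they are why kappa is optional in the fix.

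**Conclusion.** The point holds for the pairwise analysis in SAP 11.2.3 and Table 1.2.10, not for the SAP as a whole. A stated secondary objective, to estimate agreement, has no estimator, and the comparison of rates has no paired difference with an interval. On the planning figures, two very different situations (overall agreement 85.2% or 43.7%, kappa 0.43 or 0.04) would both be reported as significant, and the table would not show whether the same men are flagged.

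The figures rest on the protocol's assumed rates, on 366 men having both tests, on Wald intervals and on the uncorrected McNemar statistic. That McNemar does not measure agreement rests on none of these.

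The end point belongs to the primary outcome paper (SAP 11.1.3), and none of the secondary papers listed at the start of the SAP is described as covering agreement between the three tests, so the matter is not visibly deferred. The primary end point and the sample size are unaffected. This is an improvement available at almost no cost, not a flaw in the design.

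**What to change.** In SAP 11.2.3 and Table 1.2.10, for each pair of tests and each combination of cut-offs already listed, among men who completed both tests, report:
- the 2x2 counts;
- the paired difference in positive rate with a 95% confidence interval;
- overall, positive and negative agreement, each with a 95% confidence interval.

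Kappa with a confidence interval is optional, as already used for the MRI readers. Keep McNemar, described as the test of marginal positive rates only.

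The cost is a few more columns or a companion table, from data already collected. Fixing the measures now also avoids choosing among them after the results are known.
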